The study will be conducted in Alberta, Canada, where a single, publicly funded health authority (Alberta Health Services) delivers healthcare services, including emergency medical services (EMS) delivered by paramedics, to a population of 4.4 million people. Three levels of EMS care exist: Emergency Medical Responder (EMR), Primary Care Paramedic (PCP), and Advanced Care Paramedic (ACP). ACPS can perform advanced FBAO interventions like Magill forceps removal and intubation, while all levels receive training on basic interventions.

Study Population

Eligible patients will be adults or children aged older than 2 years who experience an out-of-hospital FBAO and are assessed by EMS or attend an emergency department for the incident. We define FBAO cases as individuals who present with a history of an object or substance not native to the airway introduced, followed by clinical signs of obstruction (e.g., stridor, cyanosis, hypoxemia, inability to move air) [3,4].

Only patients who are conscious when they receive the first FBAO intervention will be included. We will exclude cases where the patient has abnormal airway anatomy such as a tracheostomy, or who are unconscious upon receipt of first FBAO intervention.

Patient Identification

FBAO cases will be prospectively identified through two strategies:

1. A notification will be sent to researchers using Alberta Health Services' EMS electronic Patient Care Record (ePCR; Siren ePCR Version 4.6.26, Medusa Medical Technologies, Halifax, NS) when a case meets validated FBAO identification criteria based on paramedic diagnosis, protocol use, or treatment applied [4].
 - The ePCR is the sole paramedic prehospital charting system used in Alberta and therefore includes population-based data for the province, including demographics, vital signs, and standardized reporting of incident, patient, and treatment details. It also includes a free-text narrative synopsis, including information on the events preceding the FBAO, interventions performed by bystanders, patient assessments, and all interventions
2. A notification will be sent to researchers when a patient presents to an Alberta emergency department with an FBAO-related complaint (e.g., respiratory foreign body, respiratory arrest, stridor, dysphagia, cardiac arrest).

An emergency medicine physician will review identified cases to determine whether they meet the FBAO definition, based on the paramedic and emergency medicine

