documentation, vital signs, and imaging. A second physician will review 10% of cases to ensure excellent interrater reliability (Cohen's kappa > 0.8).

Patient Recruitment and Consent

Adult patients, or the primary parent(s)/caregiver(s) of pediatric patients, will be contacted by a healthcare provider not affiliated with the research team once identified as an FBAO case to seek their interest in participating by telephone. If agreeable to participate, a research assistant will subsequently follow up with the patient (or parent/caregiver) to obtain informed consent and complete a short interview for data collection.

In the case that a patient is unable to participate in an interview due to severe injury, death, or inability to be contacted, then a waiver of consent has been obtained to use the medical record for data collection.

All eligible participants will be recruited consecutively. We will conduct the pilot over a period of 6 months from November 1st, 2025, to April 30th, 2026. If we proceed with a larger effectiveness study (see Sample Size below), the research team will decide based on available resources at that time if we will immediately continue with recruitment and include the pilot study's patients in the larger study's cohort.

Data Collection

Research assistants will conduct virtual structured interviews. We will develop a standardized data collection tool and pilot it among five individuals without healthcare or research training to ensure easy comprehension. Research assistants will receive training on the data collection tool before contacting patients.

In the situation where participants are unable to be interviewed, two research team members will extract data directly from the medical record independently and in duplicate. Disagreement between data extractors will be resolved by a third researcher. Data extractor agreement will be measured using Cohen's kappa.

Variables and Analysis by Research Objective

Primary Objective: Feasibility Study

Outcome: This study's primary focus is on the feasibility of prospectively identifying and recruiting FBAO patients, with the following outcome measures:

- Number of eligible patients recruited per month (Primary)
- Proportion of eligible patients recruited (Secondary)
- Proportion of recruited patients with $\geq 90\%$ of variables collected (Secondary)

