Exposure: Given the primary aim of the feasibility study is a descriptive analysis of the outcome variables, no exposure variable is defined.

Sample Size: Abdominal thrusts and back blows are the two primary FBAO interventions used on adults and children, so the sample size is based on data of these two techniques

[3]. We estimate that 640 patients will need to be recruited to obtain 80% power using a statistical significance of 0.05 and two-sided z-test of independent proportions to detect, with successful proportion of abdominal thrusts and back blows equal to 59.5% and 72.2% respectively, with a ratio of patients who received abdominal thrusts versus back blows equal to 3.5 [3].

To complete an intervention effectiveness study in 48 months, we would need to recruit a mean of 13.3 patients per month. The slowest acceptable recruitment rate would be if recruitment required one additional year to obtain our desired sample size (60 months total). This would require recruitment of 10.6 patients per month. Using the traffic light approach for a feasibility study's sample size, we set the green criterion (progression, no concerns) to 13 patients or more per month and the red criterion (major problems, potentially not remediable concerns) to less than 10 patients per month. The amber zone will be set as 10-13 patients per month, which represents a recruitment rate range that may be compatible with a successful future study; however, we will first aim to identify and address remediable recruitment challenges before deciding whether to proceed [10].

Analysis: We will conduct a descriptive analysis of the recruited cohort's demographics, as well as the FBAO incident situational factors (categorical: frequency and proportions; continuous: medians and interquartile ranges). We will calculate the mean recruitment rate by dividing the number of recruited patients over the entire study period by the number of months recruitment was ongoing. We will track the number of patients who were eligible over the entire study period and determine our proportion of successful recruitment by dividing the count of recruited patients by the count of eligible patients. Finally, among our recruited patients, we will review the data collection forms and determine the number of patients who had 90% or more of variables obtained to ensure satisfactory data collection processes are in place.

Secondary Objectives: Effectiveness and Safety

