Outcomes: The feasibility study will inform the development of several future studies investigating the secondary objectives focusing on FBAO intervention effectiveness and safety. These objectives' outcome variables will be:

- FBAO relief: defined as successful if the responder(s) determines that the patient did not require further FBAO intervention due to improvement/resolution of their respiratory distress (Primary)
- Survival to acute care discharge (e.g., Emergency Medical Services [EMS], emergency department, or hospital discharge). If transferred to a long-term care facility due to permanent neurological function decline, we will still consider this an acute care discharge (Secondary)
- Survival to discharge with favourable neurological outcome (Secondary): defined as the patient being able to be discharged to their previous home environment, with the ability to perform the same activities of daily living as before the FBAO incident
- Intervention-associated injuries (Secondary)

Question One: Among conscious adults and children with an out-of-hospital FBAO, which initial BLS FBAO intervention is more effective and safer?

- Exposure: Initial FBAO intervention (abdominal thrusts, back blows, chest compressions)

Question Two: Among conscious adults and children with an out-of-hospital FBAO who failed initial management, is continuing the same BLS intervention more effective than changing interventions?

- Population: Adults who experience an out-of-hospital FBAO and are attended by EMS or present to the emergency department in Alberta, Canada, and received at least 5 initial interventions (e.g., 5 abdominal thrusts)
 - For this question, we will require the patient received at least 5 unsuccessful initial interventions to capture only patients who do not respond immediately to initial treatment and require further intervention.
 - After 5 initial interventions, resuscitation guidelines recommend either continuing the initial intervention (Heart and Stroke Canada, and American Heart Association [5]) or alternating to another technique (European Resuscitation Council, Canadian Red Cross, and Lifesaving Society Canada [6-9]). By excluding the patients that initially responded to 5 or less attempts, we are creating a more similar patient population when comparing alternating techniques (e.g., abdominal thrusts and back blows) versus those who continued the same technique (e.g., 20 abdominal thrusts) to help address resuscitation time bias.

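### The traffic-light cut-offs are built on 640 abdominal-thrust or back-blow patients, but the rate judged against them counts recruits with any first intervention, so the light can read too favourably.

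*Combined protocol and SAP*

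**What the plan says.** The Sample Size paragraph under the primary objective starts from the statement that "Abdominal thrusts and back blows are the two primary FBAO interventions used on adults and children" and bases the calculation on those two alone. It continues: "We estimate that 640 patients will need to be recruited to obtain 80% power", for a two-sided z-test at 0.05 with success proportions of 59.5% (abdominal thrusts) and 72.2% (back blows) and a 3.5 to 1 ratio. Spreading the 640 over 48 and 60 months gives the stated 13.3 and 10.6 per month. From these, "we set the green criterion (progression, no concerns) to 13 patients or more per month"; red is below 10, and amber lies between.

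The Analysis paragraph computes the rate by "dividing the number of recruited patients over the entire study period by the number of months recruitment was ongoing". The primary feasibility outcome is likewise the monthly number of eligible recruits, without reference to technique. Under Study Population, "Only patients who are conscious when they receive the first FBAO intervention will be included"; the type of that intervention is not restricted. Under Patient Recruitment and Consent, "All eligible participants will be recruited consecutively". Question One has chest compressions as a third exposure group. The Covariates table also allows suction devices, other and unknown as the first intervention by a bystander or a paramedic.

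**The concern.** The threshold and the quantity compared with it refer to different populations. A patient first treated with chest compressions is a proper recruit for the feasibility aim and for the effectiveness questions, but belongs to neither arm of the comparison that 640 was calculated for. A patient whose first technique is unknown cannot be placed in either arm as the plan stands. Each such recruit raises the judged rate without bringing the powered comparison closer.

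The progression decision is at stake. A green light is defined as having no concerns, and the plan allows recruitment to run straight on into the larger study with pilot patients included. A green reading that is really amber for the powered comparison would start a study likely to run longer, or with less power, than the cut-offs were meant to secure. The Analysis text for the secondary objectives will tabulate patients by exposure, but nothing connects that table to the light, and the Sample Size paragraph has no adjustment or re-estimation step.

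**Working it through.** **Inputs from the Sample Size paragraph:** p1 = 0.722 (back blows), p2 = 0.595 (abdominal thrusts), k = 3.5, two-sided alpha 0.05, power 80%, durations of 48 and 60 months, cut-offs 13 and 10. The pilot lasts 6 months (Patient Recruitment and Consent).

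**Reproducing 640.** For the pooled z-test without continuity correction, the back-blow group needs

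n = [1.96·√(p̄(1−p̄)(1+1/k)) + 0.84·√(p1(1−p1) + p2(1−p2)/k)]² / (p1−p2)², with p̄ = (p1 + k·p2)/(1+k).

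This gives 142.1 back-blow and 497.3 abdominal-thrust patients, 639.4 in all. Power at exactly 640 is 80.0%. The two arms therefore use up the whole 640, with no inflation. The rates follow: 640/48 = 13.33 and 640/60 = 10.67 (the plan prints 10.6).

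**Effect of other recruits.** Let u be the share of recruits whose first intervention is neither technique or is unknown. The documents do not give u; 5, 10 and 20% are assumptions. The power row holds the 3.5 ratio fixed.

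| Quantity | Formula | u = 5% | u = 10% | u = 20% |
|---|---|---|---|---|
| Two-group patients among 640 recruits | 640(1−u) | 608 | 576 | 512 |
| Power with that number | pooled z-test | 77.9% | 75.6% | 70.4% |
| Recruits needed for 640 in the two groups | 640/(1−u) | 674 | 712 | 800 |
| Two-group rate when the reading is 13.0 | 13(1−u) | 12.4 | 11.7 | 10.4 |
| Months to 640 in the two groups at 13 per month | 640/[13(1−u)] | 51.8 | 54.7 | 61.5 |
| Reading needed for a true green | 13/(1−u) | 13.7 | 14.4 | 16.25 |
| 6-month counts that change green to amber | 78 up to below 78/(1−u) | 78–82 | 78–86 | 78–97 |
| 6-month counts that change amber to red | 60 up to below 60/(1−u) | 60–63 | 60–66 | 60–74 |

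With u = 0, 13 per month takes 640/13 = 49.2 months.

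**Break-even against the 60-month limit.** At 13 per month the limit is missed when u exceeds 1 − 640/(13 × 60) = 17.9%. If pilot patients are included and the clock starts after the pilot, the figure is 1 − 640/(13 × 66) = 25.4%.

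**Scale of sampling noise.** The exact Poisson 95% interval for 78 recruits in 6 months is 10.3 to 16.2 per month.

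**The case against.** The strongest reply is about size. The only statement on frequency in the documents calls the two techniques the primary ones, which suggests a small remainder; options on a form show what can be recorded, not how often it occurs. At 5 to 10%, a rate of 13 per month still reaches 640 in 51.8 to 54.7 months, inside the plan's 60-month limit. If pilot patients count and the clock starts after the pilot, even 48 months is met up to a share of 1 − 640/(13 × 54) = 8.8%. The plan's own rounding already tolerates shortfalls of this order: 13 × 48 = 624 and 10 × 60 = 600. All of this stands, and it limits the importance of the point without removing the mismatch.

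Second, power also depends on the allocation ratio. By the same formula the two-group total is about 609 at a ratio of 3.2, 579 at 2.9 and 691 at 4.0, so a modest change in ratio could offset or add to a 5 to 10% loss. That is correct. The one-way direction is therefore a claim about accrual to the two groups, not about power whatever the ratio.

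Third, amber calls for remedying recruitment problems, and technique mix is not one; reporting the two-technique rate beside an unchanged light would carry the same information. It would, but the stated rule would still be applied to the wrong count. The poor fit with amber is a real drawback and should be acknowledged in the report.

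Lastly, the share will be visible in the exposure table before a larger study is designed. That helps only if someone carries it back to the cut-offs, and the plan does not say so.

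**Conclusion.** The concern holds. The cut-offs derive from a total made up entirely of abdominal-thrust and back-blow patients, while the rate compared with them includes everyone recruited. Relative to accrual for the powered comparison, the error can go only in the favourable direction. Its size cannot be found from the documents and may be small: at an assumed 5 to 10% outside the two techniques it is minor beside sampling noise, though unlike noise it never goes the other way. It becomes serious above about 18%, where a reading of exactly 13 per month would miss the plan's own 60-month limit (about 25% if pilot patients are carried over and the clock starts after the pilot). Only readings close to a boundary change colour, but those are the readings for which the rule exists. This should be corrected; it does not undermine the pilot.

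**What to change.** Keep the monthly number of all eligible recruits as the reported primary outcome. Add one sentence to the progression rule: the green, amber and red cut-offs are applied to recruits whose first intervention was abdominal thrusts or back blows (equivalently, the cut-offs are divided by the observed share of such recruits), and both rates are reported side by side. A rate further restricted to patients with known relief status can be shown as a sensitivity figure only, because the plan leaves imputation for future studies open.

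The cost is one extra count from a field already collected. A borderline green may become amber; if that happens only because of technique mix, the report should say so, since amber's stated response is aimed at recruitment problems. The observed share will be imprecise with about 78 recruits: Wilson 95% intervals are 88 to 98% for 74/78, 81 to 95% for 70/78 and 69 to 87% for 62/78.

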- Exposure: Receiving a single BLS FBAO intervention versus an intervention combination (abdominal thrusts [AT], back blows [BB], chest compressions [CC], AT and BB, AT and CC, BB and CC) after an initial 5 attempts

Question Three: Among conscious adults and children with an out-of-hospital FBAO who failed initial management, which BLS FBAO intervention or combination of interventions is more effective and safer?

- Exposure: FBAO intervention combination (abdominal thrusts [AT], back blows [BB], chest compressions [CC], AT and BB, AT and CC, BB and CC)

Analysis: As this pilot study will be underpowered to accurately estimate precision of the outcomes, we will limit reporting of these results to a descriptive analysis. We will include descriptive statistics of the patients' demographics and FBAO incident situational factors for the total study population, as well as stratified by the exposure variable (categorical: frequency and proportions; continuous: medians and interquartile ranges). We will also report descriptively the outcome variables listed above.

We will summarize missingness of all variables to determine appropriateness of imputation for future studies.

We will perform similar analyses for several subgroups: adults (aged ≥ 13 years), children (aged 3-12 years), patients residing in long-term care, patients with limited mobility, and patients who received first intervention with bystanders versus paramedics.

Covariates

Variable Name	Variable Type	Possible Values
Patient		
Age	Continuous	0 - 100
Sex	Categorical	Male, Female, Other
Estimated Patient Weight	Numerical	
Estimated Patient Height	Numerical	
History of Choking	Categorical	Yes, No, Unknown
Medical Comorbidities	Open response	Free Text
Specifically ask: Stroke, Dementia or Alzheimer's, Difficulty Swallowing or Chewing, Parkinson's Disease	List, select all that apply	Any of the specific answers
Pre-FBAO ADL Independence	Categorical	Independent, Dependent, Unknown
If Dependent: Which ADLs require assistance? Which ADLs are completely dependent?	List, select all that apply	Ambulation/mobility, Eating/feeding, Personal hygiene/bathing, Dressing, Toileting
If Limited Mobility: What is their mobility?	Categorical	Walk independent, Uses cane, Uses walker, Uses wheelchair, Limited to bed
Long term care resident	Categorical	Yes, No, Unknown
Situation		
Location	Categorical	Home, Long term care residence, Restaurant, School, Other public place, Unknown

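### Question Two: the Population line leaves out children, and the single-versus-combination exposure is ambiguous about who continued, who changed, and when that is decided

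*Combined protocol and SAP*

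**What the plan says.** All places are in the combined protocol and SAP.

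- **What is asked** (second question under Secondary Objectives): "Among conscious adults and children with an out-of-hospital FBAO who failed initial management, is continuing the same BLS intervention more effective than changing interventions".
- **Line defining the population** under that question: "Population: Adults who experience an out-of-hospital FBAO and are attended by EMS or present to the emergency department". It also requires at least five initial attempts, and its first sub-bullet requires that they were unsuccessful.
- **Rationale** (second sub-bullet): guidelines diverge after five attempts, some continuing and some alternating. Early responders are excluded so that patients who alternate are compared "versus those who continued the same technique (e.g., 20 abdominal thrusts) to help address resuscitation time bias".
- **Exposure line**: "Receiving a single BLS FBAO intervention versus an intervention combination", starting after the first five attempts. It lists three single techniques and three pairs.
- **Eligibility** (Study Population): "Eligible patients will be adults or children aged older than 2 years". The subgroups in the Secondary Objectives analysis define adults as 13 or older and children as 3-12.
- **Analysis**: descriptive only. Demographics and situational factors are given overall, "as well as stratified by the exposure variable". Outcomes get a separate sentence that names no stratifier: "We will also report descriptively the outcome variables listed above".
- **Later use** (Patient Recruitment and Consent): if a larger study proceeds, the team may "include the pilot study's patients in the larger study's cohort".

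**The concern.** There are two separate faults.

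**Population.** Taken literally, the Population line removes every child aged 3-12 from a question that names children, and leaves the child subgroup of that question empty.

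**Exposure.** The question contrasts continuing with changing, but the Exposure line contrasts one technique with several. The text does not say whether the first five attempts count towards the category, or when after the fifth attempt a patient's category is fixed. Two analysts could put the same patient in opposite groups. If the category is settled by everything received, it depends partly on how long the obstruction lasted. Relief ends intervention, so a patient relieved at attempt 7 had little chance to change, while one who changes at attempt 15 has by definition failed every attempt before it. The five-failure entry rule is there to reduce this bias, but it acts only up to attempt 5.

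At stake are the Question Two population, the exposure-stratified descriptive tables, and the larger study if pilot patients are carried into it.

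**Working it through.** **1. Plan's own figures.** Question Two has no sample size or effect estimate. The 640 belongs to abdominal thrusts versus back blows. A pooled two-sided z-test with 59.5%, 72.2%, ratio 3.5, alpha 0.05 and 80% power gives 143 + 501 = 644, and power at 640 is 80.0%. It does not use the Question Two groups.

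**2. The exposure under each reading.** Take a patient with five failed back blows:

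| Course from attempt 6 | Question asked | Only attempts after the fifth count | Whole episode counts |
|---|---|---|---|
| Back blows only | continue | single | single |
| Abdominal thrusts only | change | **single** | combination |
| Thrusts, then alternating | change | combination | combination |
| Back blows to attempt 14, thrusts from 15 | continue, late change | combination | combination |

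The first reading misplaces row 2. The second agrees with the question in rows 1-3, but row 4 enters *combination* only because nine further attempts (6 to 14) failed.

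**3. Illustration of the timing problem (assumed inputs, whole-episode grouping only).** Start at the fifth failure, with no true difference between techniques.

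- r = relief per attempt: 5, 10 or 15% (assumed)
- c = proportion changing at attempt 6: 30 or 50% (assumed)
- s = later change per attempt from attempt 7, among those still obstructed and still on the first technique: 0, 1 or 2% (assumed)
- N = further attempts: 5, 10 or 15 (15 is the rationale's 20 thrusts minus the first 5)

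With a = (1 − r)(1 − s), as proportions of all patients:

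- single and relieved = (1 − c) · r · (1 − a^N)/(1 − a)
- single and never relieved = (1 − c)(1 − r) · a^(N−1)
- all relieved = 1 − (1 − r)^N; *combination* is the remainder

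Example: r = 10%, c = 50%, s = 2%, N = 15, so a = 0.9 × 0.98 = 0.882.

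- single and relieved = 0.5 × 0.1 × (1 − 0.882^15)/0.118 = 0.3593
- single and never relieved = 0.5 × 0.9 × 0.882^14 = 0.0776
- relief in *single* = 0.3593/(0.3593 + 0.0776) = 0.822
- all relieved = 1 − 0.9^15 = 0.7941
- relief in *combination* = (0.7941 − 0.3593)/(1 − 0.3593 − 0.0776) = 0.4348/0.5631 = 0.772
- false gap = 5.0 points

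In this example 12.6% of those who continued at attempt 6 change later. At s = 1% the figures are 0.808 and 0.782; at s = 0 both are 0.794.

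Range of the false gap over r and c, *single* minus *combination*, in percentage points:

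| Later change per attempt | N = 5 | N = 10 | N = 15 |
|---|---|---|---|
| 0% | 0 | 0 | 0 |
| 1% | 0.7-1.8 | 1.7-3.6 | 1.4-5.5 |
| 2% | 1.4-3.5 | 3.3-6.6 | 2.7-9.6 |

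A coarser model with much heavier switching (four further blocks of five attempts, 20-40% relief per block, 20-50% switching before each block) gives 13-34 points. The contrast between the two models shows how far the size depends on the switching rate.

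**4. Exposure fixed at attempt 6.** With no true difference, both groups have relief 1 − (1 − r)^N, which is 0.794 in the example. The gap is 0 whatever the later change rate.

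**The case against.** The intent is not in doubt. The rationale under Question Two states the continue-versus-alternate contrast, and the listed pair of thrusts and back blows matches its example of alternating. The five-attempt phrase in the Exposure line could merely restate the entry condition. This stands: a reader might infer that *single* can never mean *continue*, but on a whole-episode reading it does. The fault is ambiguity, with one natural reading that contradicts the question.

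The rationale also supplies the branch point, five failures followed by continuing or alternating. If every change happened there, the timing bias would be 0. No document gives a later-change rate.

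Little in the pilot depends on this. A reader might infer that the pilot will publish relief proportions biased by several points. The documents do not support that: no test is planned, the tables stratified by exposure are of demographics and situational factors, and the outcome sentence does not say it will be split by exposure. Carrying pilot patients forward is conditional.

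A reader might also infer that children are meant to be excluded from Question Two. The question, eligibility and subgroups all say otherwise, so this is a wording error.

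None of this removes the adults-only conflict or supplies the missing classification rule.

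**Conclusion.** The point holds as an inconsistency in the Population line and an ambiguity in the Exposure line. Followed literally, the first gives the wrong population. The second either places some changers with the continuers, or leaves the groups dependent on how long the obstruction lasted. The direction of the timing bias, favouring *single*, follows from relief ending intervention and holds wherever some patients change late. Its size is not derivable from the documents: 0 with no late change, and 0.7-9.6 points at 1-2% late change per attempt. Those figures assume equal techniques, constant relief per attempt and whole-episode grouping, and they do not apply to the reading that counts only attempts after the fifth.

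The effect on this pilot is limited to the Question Two population and its exposure-stratified tables. Settling the definition before outcomes are compared matters more for the larger study.

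**What to change.** 1. **Population:** change adults to conscious adults and children, keeping the requirement of at least five unsuccessful initial attempts and stating that at least one further attempt was made.
2. **Exposure:** define it as the same technique as the initial one, or a different one, at the first attempt after the fifth failure. Count relief from that point.
3. **Grouping by everything received:** if it is still shown, label it descriptive and not comparable between groups.

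**Cost.** This is mainly SAP wording. The Covariates table already collects technique, number of attempts and success for each intervention, so the technique at attempt 6 can be derived if the order is kept. Bystander and paramedic interventions sit in separate blocks, each with its own initial intervention, so the order across the two needs checking and a sentence should say how attempts are counted across a handover.

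**Downside.** This rule compares the next technique, not sustained strategies such as the rationale's 20 thrusts, and later changers stay in *continue*. If the sustained strategy is the target, the future study could treat change as time-varying, which needs the full ordered sequence for every patient. Confounding by prognosis remains either way.
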